Subjects will continue on their assigned dose level throughout all cycles and through maintenance. Intra-subject dose escalations are not permitted. Dose modifications are not permitted during the GS-9973 Lead-in or Cycle 1 as this is used to assess dose limiting toxicities (DLT). Following the completion of Cycle 1, if a GS-9973 related AE of Grade \geq 3 occurs, the subject will have GS-9973 held until the AE improves to Grade \leq 1 and then may resume study therapy at the prior dose (or decreased by 1 dose level after discussion with Sponsor). For subjects assigned to Dose Level 1, the decreased dose of GS-9973 will be defined as 100 mg orally twice daily.

Dose Escalation treatment schedule is outlined in the schema below:

Dose Expansion:

At the time of this amendment, there have been no DLTs in the Phase 1 portion of the study. However, due to the low response rate to ENTO + vincristine + dexamethasone in relapsed/refractory ALL patients, it has been decided not to proceed with the dose expansion (Phase 2) portion of this trial. Prior to this amendment, dose expansion had been initiated at 400 mg BID, but was subsequently closed with no subjects enrolled.

Maintenance:

	It is anticipated that most subjects who are transplant eligible will receive hematopoietic stem cell transplant (HSCT) or therapy with curative intent if a complete remission (CR) is reached. In the absence of a suitable alternative therapeutic option, subjects who obtain clinical benefit (at least partial response [PR]) after completing both cycles of induction therapy in dose escalation may continue GS-9973 at the assigned dose level during maintenance for up to 36 cycles. Subjects will continue GS-9973 and VCR at their assigned dose. GS-9973 will continue to be taken orally twice daily with VCR to be administered on Day 1 of each 28-day cycle and dexamethasone 20 mg total dose daily for 4 days (either 10 mg twice daily or 20 mg once daily) on Days 1-4 and Days 15-18 of each 28-day cycle. Bone marrow evaluations and additional central nervous system (CNS) directed therapy can be performed as clinically indicated during maintenance.
Number of Subjects Planned:	Approximately 30
Target Population:	Adult subjects with relapsed or refractory B-cell lineage ALL

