3.5.2. Guidelines for Dose Modifications

3.5.2.1. Dosing Delays/Dose Modifications Attributed to GS-9973 (beyond Cycle 1)

If the following signs or symptoms are medically manageable, they are not to be a consideration with respect to the subject's dosing or continuation on study: nausea/mild vomiting/diarrhea, drug-related fever or chills, transient and correctable laboratory test abnormalities, line associated thrombosis, or alopecia. See Appendix 3.

There will be no dose modifications during Lead-in or Cycle 1 for GS-9973, VCR, or dexamethasone. Subjects experiencing toxicity attributed to these agents during Cycle 1 requiring discontinuation of any drug shall be removed from study and will be considered a DLT.

Dose modification of GS-9973 in subsequent cycles is permitted following guidelines provided in Appendix 3. Subjects who experience a non-hematologic toxicity assessed as GS-9973 related that is Grade 3 or higher will hold dosing of GS-9973 until the toxicity resolves to \leq Grade 1, and then may resume study therapy at the prior dose through the end of the cycle (or decreased by 1 dose level after discussion with Sponsor). For subjects assigned to Dose Level 1, the decreased dose of GS-9973 will be defined as 100 mg orally twice daily. Missed doses are not to be made up.

Adverse events and laboratory abnormalities will be graded using the CTCAE, Version 4.03.

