 b Vital signs (includin least 5 minutes. c Following consent, Subjects should be specifically if there d Bone marrow aspiration of the specifical spe	adverse events contacted by pl are any AEs si	will be assessent none (or in personne stopping the	ed pre- son, if ne stud	and po necess y.	ost-dos ary) 3	e durii 0 days	ng eac (±7 d	h clin ays) a	ic visi fter th	t, and t e subje	30 (±7) ect's la) days st dos	follow e of stu	ing cor dy dru	npletic	on of t	he sub	ject's last dose	of study drug.
e CBC with different f For female subjects during Cycle 1 on I g Pharmacokinetic pe	of childbearin Day 1 (expansio pripheral blood	g potential, ser on). Pregnancy samples will b	um tes tests v e obtai	vill be ned pr	perfor e-dose	med or during	n a Da g Lea	iy 1 of d-in of	each Day	cycle 1 -7; Cy	hereaf	ter. n Day	1, 8, 2	8 and 0	Cycle	2 on D	ay 28.	PK blood sam	ples will also b
collected 1.5 hours independent of PK CSF samples will b	time point.			,			2					-	2		2			hylaxis admini	stration is
 k Subjects with EMD l Treatment with GS- m Vincristine will be a n Dexamethasone (20 dexamethasone (20 o CNS prophylaxis point 	-9973 will be c administered du) mg BID; dose mg QD or 10 r	ontinuous. GS uring Cycles 1 d for 4 days) w ng BID; dosed	-9973 and C will be for 4	should ycle 2 disper days) v	l be dis on Day used du vill be	spense ys 1, 8, uring C disper	d on I , 15, 2 Cycle	Day 28 2 and 1 on E	to ind during ay 8 a	g Mair nd Da	itenanc y 22 a	e on I nd dur	Day 1 o ring Cy	f each	cycle.	2		15. During Ma	ntenance,

Appendix 3.	Management of Clinical and Laboratory Adverse Events	

	Dosing Delays/Dose M	odifications for AEs Attributed to	GS-9973 (beyond Cycle 1)	
Adverse Event	Grade 1	Grade 2	Grade 3	Grade 4
Dermatological	Maintain current dose level and schedule.	Maintain current dose level and schedule.	Withhold dosing until ≤ Grade 1 or return to baseline. Resume dosing at current dose level. If re-challenge at current dose level results in recurrence, may resume dosing at same or lower dose level at investigator discretion.	Withhold dosing until Grade ≤1 or return to baseline. May resume at lower dose level or discontinue dosing at investigator discretion.

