Gastrointestinal Inflammation- Diarrhea	Provide anti-diarrheal (e.g., loperamide) and maintain current dose level and schedule	Provide anti-diarrheal (e.g., loperamide). Withhold dosing until Grade <1. Resume dosing at current dose level. If re-challenge results in recurrence, may resume at initial or lower dose level at investigator discretion. Consider addition of anti-inflammatory (e.g., sulfasalazine, budesonide).	Provide anti-diarrheal (e.g., loperamide). Withhold dosing until Grade ≤1 or return to baseline. Resume at lower dose level. Consider addition of anti-inflammatory (e.g., sulfasalazine, budesonide).	Provide anti-diarrheal (e.g., loperamide). Withhold dosing until Grade ≤1 or return to baseline. May resume at lower dose level or discontinue dosing at investigator discretion. Consider addition of anti-inflammatory (e.g., sulfasalazine, budesonide).
Hepatic (elevations in ALT, AST, or bilirubin)	ALT/AST<3xULN) (Direct Bilirubin<1.5xULN)	(ALT/AST>3-5xULN) (Direct Bilirubin>1.5-<3xULN)	Withhold dosing. Monitor ALT, AST, ALP, and direct bilirubin at least 1x per week until all abnormalities are Grade ≤1 or return to baseline.	Withhold dosing. Monitor ALT, AST, ALP, and direct bilirubin at least 1x per week until all abnormalities are Grade ≤ 1 or return to baseline.
	Maintain current dose level and schedule	Maintain current dose level and schedule	If direct bilirubin was Grade <3, resume dosing at same dose level. If direct bilirubin was Grade >3, resume at lower dose level.	If direct bilirubin was Grade <4, resume dosing at lower dose level. If direct bilirubin was Grade 4, discontinue dosing.

	Dosing Delays/Dose Mo	odifications f	for AEs Attributed to	GS-9973 (beyond Cy	ycle 1)		
Adverse Event	Grade 1	Grade 2		Grade 3		Grade 4	
Pneumonitis (dyspnea, cough, hypoxia and/or diffuse interstitial pattern or ground-glass opacities on chest CT and no obvious infectious cause)	Maintain current dose level and schedule. Consider Pneumocystis therapy	<1. Consider sy corticostero Pneumocys May resum		Withhold dosing unt return to baseline. May resume dosing lower dose level or o dosing at investigato	at initial or liscontinue	Withhold dosing until Grade ≤ or return to baseline. May resume dosing at initial o lower dose level or discontinue dosing at investigator discretion	

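### After some related Grade 3 or 4 events, Protocol Section 3.5.2.1 and the Synopsis let GS-9973 restart at the prior dose where Appendix 3 requires a lower dose or discontinuation, and no text says which prevails

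*Protocol*

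**What the plan says.** Three places in the protocol set the GS-9973 restart dose after a related event of Grade 3 or higher, once Cycle 1 is over.

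- **Section 3.5.2.1** covers non-hematologic events: "Subjects who experience a non-hematologic toxicity assessed as GS-9973 related that is Grade 3 or higher will hold dosing of GS-9973", and the hold lasts to resolution at Grade 1 or below. After that, the subject "may resume study therapy at the prior dose through the end of the cycle (or decreased by 1 dose level after discussion with Sponsor"). At Dose Level 1, the reduced dose is defined as 100 mg twice daily.
- **The Synopsis**, in its dose-escalation text, covers any GS-9973-related event of Grade 3 or higher. After the hold the subject "then may resume study therapy at the prior dose (or decreased by 1 dose level after discussion with Sponsor").
- **Appendix 3** has a table for adverse events attributed to GS-9973 beyond Cycle 1, with a separate instruction for each event type and grade.

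Section 3.5.2.1 refers to the appendix twice. Its paragraph on medically manageable symptoms ends "line associated thrombosis, or alopecia. See Appendix 3". Immediately before the hold-and-resume rule it says: "Dose modification of GS-9973 in subsequent cycles is permitted following guidelines provided in Appendix 3". The Synopsis paragraph does not mention Appendix 3. Neither the protocol nor the SAP states which text governs where they differ.

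**The concern.** The body text and the appendix cover the same drug, the same treatment period and the same kind of event, yet for several events they give different restart doses. An investigator working from Section 3.5.2.1 or the Synopsis could restart at full dose, with a reduction presented as the alternative that needs Sponsor discussion. An investigator working from Appendix 3 would have to reduce or stop.

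The affected rows concern toxicities that the protocol itself flags. Section 1.3.3 names the duodenum in rats, and the gastrointestinal tract among the main targets in rabbits and dogs. Section 1.2.2 reports Grade 3/4 ALT/AST elevations in 14.5% of CLL/NHL subjects at 800 mg twice daily, and Section 1.4.1 says that 400 mg of the present formulation gives similar exposure to 800 mg of the original. Hepatic events of this grade are therefore foreseeable.

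What is at stake is subject safety and consistent dosing across sites in Cycle 2 and maintenance. The DLT window closes at the end of Cycle 1, so the 3+3 decisions are untouched.

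**Working it through.** No formula applies. The check sets each Grade 3 and Grade 4 cell of the GS-9973 table in Appendix 3 beside the restart rule in Section 3.5.2.1, which is the same in every row: prior dose permitted, or one level lower after Sponsor discussion.

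| Event row in Appendix 3 | Grade | Restart dose under Appendix 3 | Prior dose excluded? |
|---|---|---|---|
| Dermatological | 3 | Current level; same or lower if it recurs | No |
| Dermatological | 4 | Lower level or discontinue | Yes |
| Gastrointestinal inflammation-diarrhea | 3 | Lower level | Yes |
| Gastrointestinal inflammation-diarrhea | 4 | Lower level or discontinue | Yes |
| Hepatic | 3 | Same level if direct bilirubin was below Grade 3; lower level if high (printed as above Grade 3) | In part |
| Hepatic | 4 | Lower level if direct bilirubin was below Grade 4; discontinue if Grade 4 | Yes |
| Pneumonitis | 3 | Initial or lower level, or discontinue | No |
| Pneumonitis | 4 | Initial or lower level, or discontinue | No |
| Other related non-hematological | 3 | Initial or lower level, or discontinue | No |
| Other related non-hematological | 4 | Initial or lower level, or discontinue | No |

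The wording of three of the excluding cells:

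- Dermatological Grade 4: "May resume at lower dose level or discontinue dosing at investigator discretion".
- Gastrointestinal Grade 3: "Resume at lower dose level. Consider addition of anti-inflammatory".
- Gastrointestinal Grade 4: "May resume at lower dose level or discontinue dosing at investigator discretion. Consider addition of anti-inflammatory".

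**Count.**

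- Cells: 5 event rows × 2 grades = 10.
- Prior dose excluded outright: 3 at Grade 4 (dermatological, gastrointestinal, hepatic) + 1 at Grade 3 (gastrointestinal) = 4.
- Excluded only when direct bilirubin is high: 1 (hepatic Grade 3).
- In conflict outright or in part: 4 + 1 = 5 of 10. Compatible: 10 − 5 = 5.

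**Two examples.** A Dose Level 1 subject with related Grade 3 diarrhea in Cycle 2 may restart at 200 mg twice daily under Section 3.5.2.1, but at 100 mg twice daily under Appendix 3. A subject whose direct bilirubin reached Grade 4 and then resolved may restart at the prior dose under the body text, but must stop under the appendix.

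**Process.** The body text makes a reduction subject to Sponsor discussion. None of the 10 cells asks for it.

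**Other safeguards.** Section 3.5.2.2 removes a subject if the toxicity recurs, or if therapy is withheld for more than 2 weeks because of related toxicity. Section 6.8 stops drug for unacceptable toxicity. Section 7.6 has treatment-emergent toxicities brought to the Medical Monitor's attention. None of these sets the dose of the first rechallenge.

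**The case against.** The best reply is that Appendix 3 already controls. The sentence just before the resume rule makes dose modification conditional on the appendix's guidelines, and the appendix table carries nearly the same heading as Section 3.5.2.1. The natural reading would then be a general rule with event-specific detail behind it. The resume rule is also permissive: it offers the reduction that Appendix 3 requires and never obliges anyone to restart. An investigator who follows Appendix 3 therefore breaches neither text, provided a reduction is also discussed with the Sponsor. With the Medical Monitor informed under Section 7.6, an unnoticed full-dose restart is less likely. Few subjects can be affected, because escalation is complete and expansion closed with nobody enrolled.

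Much of this stands. Both texts can be followed together, and the reach is small. The hepatic Grade 3 cell is also less certain than the other four, because its inequality sign may have been altered when the PDF was read.

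The objection does not remove the problem. The pointer is followed at once by a complete rule that authorizes a restart dose the appendix excludes, with no exception clause. A reader may fairly take that rule as the one for Grade 3 and above, and use the appendix only when choosing to reduce. The Synopsis lacks even the pointer. That a careful investigator can satisfy both texts does not stop another from restarting at full dose with the protocol's express permission.

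**Conclusion.** The concern holds and should be fixed. The prior dose is permitted by Section 3.5.2.1 and the Synopsis but excluded by Appendix 3 in 4 of 10 Grade 3 and 4 cells outright, and in a fifth when direct bilirubin is high. The four outright conflicts do not depend on the uncertain sign in the hepatic Grade 3 cell. Three of the four are at Grade 4, so the permission reaches full-dose rechallenge after the most severe non-fatal skin, gastrointestinal and hepatic events.

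The reach is limited to subjects treated in Cycle 2 or maintenance. Maintenance can run to 36 cycles, and the SAP Introduction says that subjects then on study would continue to be treated and/or followed. The documents do not say how many remained on drug, so the number exposed cannot be stated. DLT assessment, escalation decisions and the planned analyses are not affected.

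**What to change.** Add one clause to the resume sentence in both Section 3.5.2.1 and the Synopsis: *except where Appendix 3 requires a lower dose level or discontinuation, in which case Appendix 3 applies.*

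This introduces no new policy, because it gives effect to the stricter rule the sponsor has already written. It can be made by clarification letter or amendment, and changes no data collection, DLT rule or analysis.

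The clause does not touch the cells where Appendix 3 leaves the choice between the same and a lower dose to the investigator. There Section 3.5.2.1 would still ask for Sponsor discussion before a reduction. That difference is procedural, does not permit a dose the appendix forbids, and can stay as it is.

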1.4.1. Rationale for the GS-9973 Dose Selection

GS-9973 administered twice daily in previous studies was well tolerated up to 1200 mg (7 days in the fasted state) in healthy subjects and 900 mg (6 days in the fed state) in rheumatoid arthritis (RA) subjects. A GS-9973 dose of 800 mg twice daily is being evaluated in the Phase 2 program in subjects with CLL, indolent NHL, mantle cell lymphoma, diffuse large B-cell lymphoma, follicular lymphoma, and non-FL iNHL. Pharmacodynamic evaluation at exposures equivalent to an 800 mg twice daily dose, resulted in trough concentrations that inhibited 70-80% of Syk activity in normal healthy volunteers. In CLL patients, this level of target suppression resulted in clinical benefit.

In the current protocol, a new spray-dried dispersion (SDD) formulation will be used. With this formulation, a 400 mg dose resulted in exposures similar to the 800 mg dose of the original formulation. Among the subjects treated with GS-9973 SDD formulation (N = 28), there were no SAEs reported. In the study, 3 subjects (10.7%) had AEs resulting in study drug discontinuation. Overall, 19 subjects (67.9%) reported an AE. The most common AEs included: headache (11 subjects, 39.3%); back pain and nausea (6 subjects each, 21.4%); ALT increased, rash, and pruritus (4 subjects each, 14.3%); and (3 subjects each, 10.7%) reported AST increased and constipation. No Grade 3 or 4 AEs were reported.

Subjects enrolled in the first cohort will receive 200 mg of GS-9973 and 0.5 mg of VCR. These conservative doses were selected to minimize the potential safety risk to subjects. Nonclinical studies suggest that these low doses in combination can have anti-proliferative activity.

The doses of GS-9973 SDD proposed in the current study, from 200 mg twice daily to 400 mg twice daily, provides a wide range of daily doses (2-fold between 200 mg twice daily vs. 400 mg twice daily) to evaluate the dose/exposure/PD relationship which may be helpful in dose selection for ongoing/future GS-9973 SDD ALL studies. Vincristine will be dose escalated up to 2 mg, which is the commonly used dose cap for VCR, in combination with 400 mg of GS-9973.

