3.3.1. Dose Escalation

During dose escalation, there will be four dose levels (outlined in Table 3-1) investigated in dose escalation where subjects in cohorts of 3 to 6 will sequentially enroll into one of the dose levels using the 3+3 dose escalation design. The starting dose level for the first cohort is defined as Dose Level 1.

Dose Level	G8-9973	Vincristine (VCR)
1	200 mg BID	0.5 mg per dose
2	400 mg BID	0.5 mg per dose
3	400 mg BID	1 mg per dose
4	400 mg BID	2 mg per dose

Table 3-1.GS-9973/VCR Dose Escalation

Subjects in Dose Level 1 will receive 200 mg GS-9973 taken orally twice daily (BID). Subjects in Dose levels 2 to 4 will receive 400 mg GS-9973 orally BID. Subjects in all dose levels will receive dexamethasone 20 mg BID for four days during Cycle 1 on Days 8-11 and Days 22-25 and during Cycle 2 on Days 1-4 and Days 15-18. Each treatment cycle is 28 days in length.

In the absence of toxicity requiring a drug interruption (as defined in Section 3.5.2.1), dosing of GS-9973 will be taken continuously without interruption.

Subjects will have evaluations for safety and provide blood for drug levels prior to starting Lead-in and 1.5 hours after the first dose of GS-9973.

Additional PK blood samples will be collected at (applies to both escalation and expansion):

- Pre-dose during Cycle 1 on Day 1 and 1.5 hours (± 30 minutes) post-dose of GS-9973
- Pre-dose during Cycle 1 on Day 8, and 1.5 hours (± 30 minutes) post-dose of GS-9973
- Pre-dose during Cycle 1 on Day 28 and Cycle 2 on Day 28, and 1.5 hour (± 30 minutes) post-dose of GS-9973
- A sample of cerebrospinal fluid (CSF) for PK analysis will be taken during Cycle 1 on Day 28 and Cycle 2 on Day 28 (untimed sample) prior to CNS prophylaxis administration

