3.3.3. Maintenance

It is anticipated that most subjects will receive hematopoietic stem cell transplant (HSCT) therapy with curative intent if a complete remission (CR) is reached. In the absence of suitable alternative therapeutic options, subjects who obtain clinical benefit (at least PR) after completing both cycles of induction therapy in dose escalation may continue GS-9973 at the assigned dose level in the maintenance phase for up to 36 cycles. Subjects will continue GS-9973 and VCR at their assigned dose. GS-9973 will continue to be taken orally twice daily with VCR given on Day 1 of each 28-day cycle. Dexamethasone may be administered as a single dose of 20 mg once daily or a divided dose of 10 mg twice daily on Days 1-4 and Days 15-18 of each 28-day cycle.

Bone marrow evaluations and additional central nervous system (CNS) directed therapy can be performed as clinically indicated in the maintenance phase.

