3.5.2.2. Dose Modifications for Non-Hematologic Toxicity for VCR, and dexamethasone

If the subject experiences any non-hematologic clinically significant Grade 3 or greater toxicity felt to "possibly" be related to any agent, hold the protocol therapy until it resolves to \leq Grade 2. If related to VCR, reduce the dose of VCR to by one dose level (per Table 3-1); if at lowest dose level, resuming treatment with VCR will be at Investigator's discretion after discussion with Sponsor. Refer to product label information for specific toxicity management. If related to dexamethasone, resuming treatment with dexamethasone will be at the discretion of the Investigators. If the toxicity recurs, subject will be removed from study. If protocol therapy is withheld for more than 2 weeks for toxicity possibly, probably, or definitely related to protocol-based therapy or up to 4 weeks for any other reason, subjects will be removed from protocol.

Subjects who have been dose-reduced cannot be returned to a higher dose level.

Toxicities in an individual subject must resolve to Grade 2 or to baseline levels before proceeding with the next cycle of treatment.

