3.5.3. Dose Modifications for Hematologic Toxicity for GS-9973, VCR, and dexamethasone

It is recognized that drug-related hematologic toxicity in this population may be difficult to ascertain given the aggressive hematologic disease and the fact that multiple cycles of therapy may need to be administered for maximal clinical response. Therefore, there will be no dose modifications for hematologic toxicity due to GS-9973, VCR, or dexamethasone during Cycle 1. However, after the first cycle is administered, subjects suspected to have protocol therapy related ANC and/or platelet count toxicity (i.e. fail to recover to at least 50% of the prior cycle's baseline value), will have the dose of VCR reduced by one dose level (or 50% if at lowest dose level) dexamethasone and the dose of GS-9973 will be decreased one dose level. Dose modifications because of concern for drug induced cytopenias will be discussed with the study PIs. Dose modifications for hematologic toxicity for subjects who have achieved a CR or CRi are detailed below.

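### At Dose Levels 3 and 4, a one-level reduction read from Table 3-1 leaves GS-9973 at 400 mg BID, and no other reduced dose is stated for them

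*Protocol*

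**What the plan says.** Protocol Table 3-1 (section 3.3.1) defines four dose levels, each a GS-9973/vincristine (VCR) pair. The text below it confirms the GS-9973 column: "Subjects in Dose levels 2 to 4 will receive 400 mg GS-9973 orally BID". Level 1 receives 200 mg BID.

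Reductions after Cycle 1 are expressed in these levels:

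- **Synopsis and 3.5.2.1 (GS-9973-related toxicity, Grade 3 or higher).** The synopsis says the subject "may resume study therapy at the prior dose (or decreased by 1 dose level after discussion with Sponsor"), and 3.5.2.1 repeats the rule for non-hematologic toxicity, allowing the prior dose "through the end of the cycle (or decreased by 1 dose level after discussion with Sponsor"). Both then give 100 mg BID as the reduced dose for subjects assigned to Dose Level 1. No amount is given for the other levels.
- **3.5.2.2 (VCR, non-hematologic).** The instruction is to "reduce the dose of VCR to by one dose level (per Table 3-1").
- **3.5.3 (hematologic).** VCR goes down one level, or by 50% if already at the lowest, and "the dose of GS-9973 will be decreased one dose level".
- **3.5.3.1 and 3.5.3.2 (neutropenia, thrombocytopenia).** GS-9973 and VCR are stepped down together by one level, with 100 mg BID again given for Level 1 only.
- **Appendix 3.** The GS-9973 table refers to a lower dose level without an amount. The VCR and dexamethasone tables give the reduction as 50%.

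**The concern.** A dose-reduction rule should lower the drug it names. If a dose level is a row of Table 3-1, the rule does so for GS-9973 at Level 2 and, through the separate 100 mg provision, at Level 1. At Levels 3 and 4 it does not: the row below carries the same GS-9973 dose.

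A site applying the table literally could then restart the suspected drug at full dose after an event for which the protocol requires less, and record the subject as reduced by one level. Such a site would have no obvious reason to query it.

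**Working it through.** No sample size, power or error rate enters, and the plan states no figure to reproduce. The check is a look-up in Table 3-1, moving each level down one row.

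| Assigned level | GS-9973 BID, before to after | Change | VCR per dose, before to after | Change |
|---|---|---|---|---|
| 4 (to 3) | 400 to 400 mg | 0% | 2 to 1 mg | -50% |
| 3 (to 2) | 400 to 400 mg | 0% | 1 to 0.5 mg | -50% |
| 2 (to 1) | 400 to 200 mg | -50% | 0.5 to 0.5 mg | 0% |
| 1 (stated separately) | 200 to 100 mg | -50% | not in Table 3-1 | n/a |

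**GS-9973 at Levels 3 and 4, two readings**

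- Table row: 2 x 400 = 800 mg/day; over a 28-day cycle, 800 x 28 = 22,400 mg (no reduction).
- Per-drug step: 2 x 200 = 400 mg/day; 400 x 28 = 11,200 mg (50% lower).

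These are prescribed doses, not estimates of exposure or risk.

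**Paired rules in maintenance.** Section 3.3.3 says "GS-9973 will continue to be taken orally twice daily with VCR given on Day 1 of each 28-day cycle", so there is one VCR dose per cycle. The row step removes 2 - 1 = 1 mg of VCR per cycle at Level 4, or 1 - 0.5 = 0.5 mg at Level 3, and no GS-9973.

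**Where a decrease is required**

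1. Section 3.5.3, and 3.5.3.1 and 3.5.3.2 beneath it, word the decrease as mandatory. The two subsections are introduced as applying to subjects in CR or CRi, and 3.5.3.2 starts only with the second maintenance cycle.
2. In the Appendix 3 GS-9973 table, five situations allow restart only at a lower level:
   - Grade 4 dermatological (discontinuation is also allowed);
   - Grade 3 diarrhea;
   - Grade 4 diarrhea (discontinuation is also allowed);
   - Grade 3 hepatic, when direct bilirubin meets the trigger, printed as greater than Grade 3;
   - Grade 4 hepatic, when direct bilirubin was below Grade 4.

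The Grade 3 and 4 pneumonitis and other non-hematologic cells allow the initial or a lower dose, so they are not counted.

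**Where it is not required.** Under 3.5.2.1, restart at the prior dose is allowed outright, and a decrease follows discussion with the Sponsor.

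**The case against.** The strongest reply is that the row reading defeats the text's own purpose. Section 3.5.2.1 contrasts the prior dose with a decreased one; at Levels 3 and 4 the row reading makes these the same GS-9973 dose. Section 3.5.3 says the GS-9973 dose is decreased, and 400 to 400 is no decrease. Appendix 3 uses dose level for dexamethasone, which has no column in Table 3-1, so there the term must mean the drug's own dose. Section 1.4.1 describes the GS-9973 range as "from 200 mg twice daily to 400 mg twice daily", and a special number for Level 1 alone makes sense if 200 mg BID is the bottom of a per-drug ladder.

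This stands as evidence of intent: a step to 200 mg BID is probably what is meant. It does not supply the missing statement. Right after its reduction rule, 3.5.2.1 uses Dose Level 1 as a row of Table 3-1; 3.5.2.2 sends the reader to that table for one level; and 3.5.3.1 and 3.5.3.2 move the two drugs as a pair, which is how the rows are built.

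The safeguards also count. Beyond the Sponsor discussion in 3.5.2.1, section 3.5.3 says "Dose modifications because of concern for drug induced cytopenias will be discussed with the study PIs", and 7.6 directs toxicity questions to the Medical Monitor. They make a wrong restart less likely, but they do not define the dose, and the five Appendix 3 situations do not themselves call for Sponsor discussion.

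A reader might infer more than the documents support:

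- **That every 400 mg BID restart after a Grade 3 event is an error.** It is not; 3.5.2.1 permits it.
- **That any raised direct bilirubin in the Grade 3 hepatic cell forces a lower dose.** It does not. Below Grade 3 the subject resumes at the same dose. The printed trigger is greater than Grade 3; whether a greater-or-equal sign was lost in text extraction cannot be told.
- **That subjects were in fact restarted at the wrong dose.** Nothing in the documents shows this.

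**Conclusion.** The point holds as a gap in the reduction rule. Read literally, a one-level step at Levels 3 and 4 lowers GS-9973 by 0%, against 50% on the probably intended reading (800 versus 400 mg/day). Level 2 is unambiguous at 200 mg BID, and Level 1 has its own stated dose.

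The conclusion rests on Table 3-1 being the only written definition of a dose level, which is so in both documents.

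The reach is narrow. The rule acts only after Cycle 1, so DLT evaluation, the MTD and the sample size are untouched. Escalation is complete and expansion closed with no subjects enrolled (3.3, 3.3.2). What remains is subjects still on treatment: SAP section 1 says those on study continue to be treated or followed, and maintenance may run to 36 cycles. The planning assumption put 6 + 6 = 12 of 18 evaluable subjects at Levels 3 and 4 (8.9), but the documents do not say how many remain on treatment; the number is likely small. The SAP already lists dose modifications by subject (4.2.2) and summarizes adverse events leading to reductions by drug (7.1.6.1), so it needs no change.

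**What to change.** Add one statement, for example a footnote to Table 3-1 referenced in 3.5.2.1, 3.5.3 (covering its subsections) and Appendix 3: a one-level reduction of GS-9973 is 400 to 200 mg BID for subjects assigned to Levels 2 to 4, and 200 to 100 mg BID for Level 1, independent of the VCR step.

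The cost is a clarifying sentence and its cross-references. It needs no new data, visits or subjects, and no SAP change. Whether Levels 2 to 4 may take a second step to 100 mg BID is a separate question that this point does not depend on.
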